5.3.4 Physical Examination

Complete and/or interim physical examinations may be performed by a Doctor of Medicine (MD), or someone who is authorized to perform the examinations by training and has been delegated this task by the principal investigator. While the interim physical examination may not be as comprehensive as the initial full examination, key aspects of the interim examination should evaluate important body systems as clinically indicated. These body systems can include lymph nodes, liver, spleen, and breast at the discretion of the examiner. An interim physical examination may note any changes in the subject's condition (body systems) since the last assessment and does not preclude examination of any of the body systems as clinically indicated.

Every effort should be made to ensure the same evaluator will complete the physical examination for each subject at all visits throughout the study. Documentation of who performed the examination is to be recorded in source notes.

5.4 Efficacy Assessments

Clinical assessments of response should be performed by the same assessor(s) and at approximately the same time of day throughout the duration of the study.

5.4.1 Primary Efficacy Assessment

5.4.1.1 Short-Term Period

Primary efficacy assessment is a composite endpoint, the BICLA, which includes BILAG-2004, SLEDAI-2K (30 day)²⁰, Physician Global Assessment of disease activity (MDGA) and no treatment failure. The BILAG-2004 index was selected as the central score on the basis of its comprehensiveness, ability to capture partial improvement, and the clinical relevance of its scoring system. BILAG assessments will be performed by the investigators, and grades will be determined by an independent central reader group.

5.4.1.2 Long-Term Extension Period

Primary efficacy assessments during the long-term extension will be the same as in the short-term period, in order to assess long-term durability of response.

5.4.2 Secondary Efficacy Assessments

5.4.2.1 Short-Term Period

Training and instruction on BILAG 2004 index assessment will be provided and discussed at the Investigator's Meeting or at workshops. The response measure (BILAG) will be reviewed and discussed with the investigational staff at the Investigator Meeting or other forum as a method of standardizing the grading between the investigational staffs. All Investigative site personnel performing BILAG evaluations must be trained and certified.

The BILAG index measures and reports disease activity in different organs/systems separately. The BILAG score is calculated for each of nine systems depending on the clinical features

present and whether they are new, worse, the same or improving in the last 4 weeks compared with previously. A BILAG “A” represents the presence of one or more serious features of lupus. A BILAG “B” represents more moderate features of the disease. A BILAG “C” includes only mild symptomatic features. A BILAG “D” represents only prior activity with no current symptoms due to active lupus. A BILAG “E” represents an organ that has never been involved. Assessments used to determine BILAG score must be performed by the Investigator, or a BILAG certified (an individual who has passed the BMS sponsored BILAG Certification Test) Sub-Investigator. The Sub-Investigator may be a Doctor of Medicine (MD), or someone who is authorized to perform the examinations by training and has been delegated this task by the principal investigator. Changes in therapy based on any clinical or laboratory assessment must be approved by the Investigator or a MD/DO Sub-Investigator.

5.4.2.2 *Long-Term Extension Period*

Secondary efficacy assessments during the long-term extension will be the same as in the short-term period, in order to assess long-term durability of response.

5.5 Pharmacokinetic Assessments

5.5.1 *Short-Term Period*

Pharmacokinetics of BMS-931699 will be derived from serum concentration versus time data.

The pharmacokinetic parameters to be reported include C_{trough} (ng/mL), which will be measured from serum samples collected as defined [Table 5.5.3](#).

Additional blood samples will be obtained according to [Table 5.5.3](#), which specifies pre-dose samples as well as post-dose samples on Day 46 and Day 48. If both post-dose samples cannot be obtained at these times (ie, Days 46 + Day 48), the 2 samples may be obtained on (Days 60 + Day 62) OR (Days 74 + Day 76).

Population PK (PPK) analysis maybe performed using PK data from the current proposed study in SLE patients. Results of the PPK analysis may also be used to characterize the exposure-response (E-R) relationship in BMS-931699 by means of the individual model predicted exposure and efficacy/safety data. Further, the effect of covariates (demographic and clinical) on efficacy/safety may be explored in the E-R analyses. Results of the PPK and E-R analyses will be reported separately if performed.

5.5.2 *Long-Term Extension Period*

Immunogenicity and PK blood samples will be obtained every three months during the LTE period.

5.5.3 Pharmacokinetics: Collection and Processing

Table 5.5.3 lists the sampling schedule to be followed for the assessment of pharmacokinetics. Further details of blood collection and processing will be provided to the site in the procedure manual.

Table 5.5.3: Pharmacokinetic Sampling Schedule for BMS-931699

Study Day of Sample Collection	Event	Time (Relative To BMS-931699 Dose) Hour: Min	BMS-931699 Pharmacokinetic Blood Sample	BMS-931699 Immunogenicity Sample
1	Pre-dose	00:00	X	X
15	Pre-dose	00:00	X	X
29	Pre-dose	00:00	X	X
43	Pre-dose	00:00	X	
46 (± 1 day) ^a		72:00	X	
48 (± 1 day) ^a		120:00	X	
50	Pre-dose	00:00	X	
57	Pre-dose	00:00	X	
64	Pre-dose	00:00	X	
71	Pre-dose	00:00	X	
78	Pre-dose	00:00	X	
85	Pre-dose	00:00	X	X
113	Pre-dose	00:00	X	
141	Pre-dose	00:00	X	
169/End of Treatment		168:00	X	X
Long-term extension	Pre-dose	Every 3 months	X	X
Follow up Day 42 after EOT		42 Days after end of treatment	X	X
AE ^b			X	X

^a Day 46 and Day 48 post-dose PK samples are planned for the same dosing interval. A dosing interval is the time between two doses, in this study, dosing interval is a week. Sites should plan ahead with patients to ensure these samples are collected during the same dosing interval. If patients cannot have post-dose PK samples collected on Day 46 and Day 48, the 2 samples may be obtained on (Day 60 +Day 62) OR (Day 74 + Day 76). The exact dosing time and sampling time should be recorded accordingly.

^b PK and immunogenicity samples to be drawn for subjects who experience an AE leading to discontinuation of study treatment.

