*Subjects who are receiving mycophenolic acid/mycophenolate mofetil may participate in the study only if mycophenolate mofetil therapy is given as a maintenance therapy and up to a maximum of 2 g/day (or mycophenoate acid dose equivalent); in subjects of African ancestry, 3 g/day (or mycophenoate acid dose equivalent) may be administered at the Investigator’s discretion.

v) Prednisone is not required; however, if subject is taking prednisone (or prednisone-equivalent), dose cannot exceed 30 mg/day at screening for a subject to be eligible and must be stable at a maximum of 10 mg/day for at least 5 days prior to Day 1 (randomization). Refer to Appendix 1 for a list of prednisone-equivalents.

vi) Any other immunosuppressive or biologic drug will require washout periods indicated in Appendix 2 prior to signing consent.

vii) If subjects receive chronic therapy with NSAIDs (including marketed COX-2 inhibitors), doses must be stable for 14 days prior to first dose of study medication on Day 1 (randomization) and are recommended to remain stable throughout the study.

Note: NSAIDs should be withheld for at least 12 hours prior to visits where BILAG, SLEDAI 2K, joint counts, CLASI and MDGA will be assessed.

3. Age and Reproductive Status

- a) Males and Females, ages 18 to 70 years, inclusive
- b) Women of childbearing potential (WOCBP) must have a negative serum or urine pregnancy test (minimum sensitivity 25 IU/L or equivalent units of HCG) within 24 hours prior to the start of study drug.
- c) Women must not be breastfeeding
- d) WOCBP must agree to follow instructions for method(s) of contraception for the duration of treatment with study drug(s) BMS-931699 plus 5 half-lives of study drug

BMS-931699 (7 days) plus 30 days (duration of ovulatory cycle) for a total of 65 days post-treatment completion.

- e) Males who are sexually active with WOCBP must agree to follow instructions for method(s) of contraception for the duration of treatment with study drug(s) BMS-931699 plus 5 half-lives of the study drug (7 days) plus 90 days (duration of sperm turnover) for a total of 125 days post-treatment completion.
- f) Azoospermic males and WOCBP who are continuously not heterosexually active are exempt from contraceptive requirements. However they must still undergo pregnancy testing as described in this section.

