4.5 Selection and Timing of Dose for Each Subject

4.5.1 *Double-blind Administration of BMS-931699 or Placebo*

On Day 1, subjects will be randomized to one of the following dosing arms in a 1:1:1:1:1 randomization scheme:

- BMS-931699 at 12.5 mg weekly sub-cutaneous (SC) injection
- BMS-931699 at 12.5 mg every other week (EOW) SC injection
- BMS-931699 at 5 mg EOW SC injection
- BMS-931699 at 1.25 mg EOW SC injection
- Placebo SC injection (short-term period only)

The Pharmacist (or qualified drug preparation person) will know the randomized assignments and will prepare the appropriate dose of active BMS-931699 or placebo accordingly. The prepared drug must be supplied to study personnel in a manner such that neither study personnel nor subjects will be aware of whether they receive active drug or placebo.

Every randomized subject will be required to come to the clinic/research center weekly to be dosed. This will ensure double-blind is maintained despite the variability of regimens. Subjects randomized to weekly subcutaneous injections of either placebo or BMS-931699 will be dosed weekly as per schedule and subjects randomized to one of the every other week arms will be alternating between receiving a subcutaneous injection of BMS-931699 one week and one of placebo the following week.

Every randomized subject will be required to remain on site for at least 1 hour after each dose to ensure safety.

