**7.7 Pharmacokinetic Analysis**

Summary statistics of Ctrough (mean, SD, geometric mean, % CV, median, min, and max) for the PK analysis population will be provided by treatment and study day.

Similar statistics will be provided for post-dose concentration on Day 46 and Day 48.

The listing of Concentration of BMS-931699 by treatment and study day will also be provided.

[REDACTED]

[REDACTED]

[REDACTED]

[REDACTED]

[REDACTED]

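### Table 5.5.3 gives every arm a one-week BMS-931699 interval, so mid-interval samples (Days 50, 64, 78) in the three every-other-week arms would, by inference, be summarised as Ctrough

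*Protocol*

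**What the plan says.** Protocol 4.5.1 sets four active regimens: 12.5 mg weekly, and 12.5 mg, 5 mg and 1.25 mg every other week (EOW). To keep the blind every subject is injected weekly, and those in the "every other week arms will be alternating between receiving a subcutaneous injection of BMS-931699 one week and one of placebo the following week". SAP 2.2 and 6.2 repeat this.

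Table 5.5.3 does not distinguish the arms. Its time column is headed "Time (Relative To BMS-931699 Dose) Hour: Min". Days 15, 29, 43, 50, 57, 64, 71, 78, 85, 113 and 141 are all pre-dose at 00:00, Days 46 and 48 are 72:00 and 120:00, and Day 169 is 168:00. Footnote a adds "A dosing interval is the time between two doses, in this study, dosing interval is a week".

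Protocol 5.5.1 names Ctrough as the PK parameter, "which will be measured from serum samples collected as defined" in Table 5.5.3. SAP 4.4 defines the endpoint at the time points of protocol Section 5.5. Under SAP 7.7, Ctrough statistics "for the PK analysis population will be provided by treatment and study day", and the only samples given their own post-dose summary are Days 46 and 48.

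**The concern.** In an EOW arm the end of the active dosing interval comes 14 days after the last active injection. A sample taken before the Day 50, 64 or 78 injection precedes placebo and falls halfway through that interval. No passage restricts Ctrough in the EOW arms to the end of the two-week interval, so a programmer following the table would put these samples under the Ctrough heading.

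Ctrough is the only PK endpoint listed for the short-term period. In the EOW arms its profile by study day would rise and fall for no reason but sampling phase, and on the mid-interval days the difference from the weekly arm would look smaller than it is. SAP 7.11.4 also allows individual plots of Ctrough with anti-drug-antibody status, where the same swings could be misread.

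**Working it through.** **Inputs.** Alternating schedule: Protocol 4.5.1. Sampling days and nominal hours: Table 5.5.3. Half-life: Protocol 3.3.1, criterion 3e, "plus 5 half-lives of the study drug (7 days"; its total confirms the reading, since 5 × 7 + 90 = 125 days.

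**Active-dose days.** Weekly arm: 1 + 7k, last before Day 169 = Day 162. EOW arms, active first on Day 1: 1 + 14k, that is 1, 15, 29, 43, 57, 71, 85 … 155. Starting with active drug is implied by the order of the alternation wording and by the table's own hours. If placebo came first, the last active dose before Day 46 would be Day 36, and Day 46 would be (46 − 36) × 24 = 240 h, not 72 h.

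**The table's own hours.**
- Day 46: (46 − 43) × 24 = 72 h. Day 48: (48 − 43) × 24 = 120 h. Both reproduce in every active arm.
- Day 169, weekly arm: (169 − 162) × 24 = 168 h. Reproduces.
- Day 169, EOW arms: (169 − 155) × 24 = 336 h. The stated 168:00 does not reproduce.

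**Hours since last active dose at the pre-dose samples.**

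| Day | 43 | 50 | 57 | 64 | 71 | 78 | 85 |
|---|---|---|---|---|---|---|---|
| Weekly arm | 168 | 168 | 168 | 168 | 168 | 168 | 168 |
| EOW arms | 336 | 168 | 336 | 168 | 336 | 168 | 336 |

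Days 15, 29, 113 and 141 are also 336 h in the EOW arms. Pre-dose samples on Days 15 to 141 number 11; three of them (50, 64, 78) are mid-interval in each EOW arm.

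**Size.** With log-linear decline, C(7 d)/C(14 d) = 2^(7/t½).
- t½ = 7 days (protocol): 2^1 = 2.0.
- t½ = 10 days (assumed): 2^0.7 = 1.6.
- t½ = 5 days (assumed): 2^1.4 = 2.6.

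A one-compartment subcutaneous steady-state model with t½ = 7 days gives 2.0 down to 1.6 for assumed absorption half-lives of 0.5 to 3 days.

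**Comparison with the weekly arm.** Take equal 12.5 mg doses at steady state with t½ = 7 days and log-linear decline. In units of one dose's initial concentration:
- weekly trough: 0.5/(1 − 0.5) = 1.00
- EOW level at 7 days: 0.5/(1 − 0.25) = 0.67
- EOW trough at 14 days: 0.25/(1 − 0.25) = 0.33

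The weekly-to-EOW ratio is therefore 3.0 on true trough days and 1.5 on Days 50, 64 and 78.

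**The case against.** The strongest reply is that the mislabelling is inferred. Neither document names Days 50, 64 or 78 as Ctrough. The word trough must restrict the set to some extent, because Table 5.5.3 also contains a Day 1 baseline, a follow-up sample and samples triggered by adverse events. The PK row of Table 5.1-2 lists only Days 1, 15, 29, 57, 85, 113, 141 and 169 on treatment, and each of these after Day 1 is a true 14-day trough in the EOW arms. Footnote a can be read as an instruction to blinded sites, who see weekly injections, to keep the Day 46 and Day 48 samples in one interval. This stands as a limit on certainty. It does not supply a rule: Table 5.1-2 refers to Table 5.5.3 for the additional collections, that table calls the three days pre-dose relative to the BMS-931699 dose, and the SAP sets aside only Days 46 and 48.

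A reader might infer more than the documents support:
- **Pooling.** SAP 7.7 summarises by treatment and by study day, so mid-interval levels are not averaged with troughs or across arms. The fault is in the label of certain rows and in comparisons made on those days.
- **Exposure-response.** Protocol 5.5.1 bases the main exposure-response work, if done, on individual model-predicted exposure, and footnote a asks for actual dosing and sampling times. A mid-interval sample is valid data for such a model, provided placebo injections are not coded as doses. For the possible exploratory analysis at the Day 85 interim, neither document says that observed Ctrough would be used.
- **Day 169.** This sample is a true EOW trough. Only its nominal hour is wrong, and no analysis shown in the SAP uses that hour.

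The PK sub-study (SAP 7.11.6) does treat the three arms as two-weekly regimens. It is voluntary, aims for about 4 subjects per arm in the short-term period, and does not govern the main Ctrough summary.

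**Conclusion.** The point holds as an inconsistency between Table 5.5.3 and the EOW schedule, with a probable consequence for one descriptive endpoint. Read as written, the plan would put 3 of 11 pre-dose samples per EOW arm under Ctrough at about twice the true trough (1.6 to 2.6 over the assumed half-lives), giving an artificial alternation between Day 43 and Day 85. This rests on active drug being given first on Day 1, approximately log-linear decline between 7 and 14 days, and the inference that the three days are counted as Ctrough.

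The effect stops at the Ctrough summaries and any Ctrough plots. BICLA, its power, and model-based exposure-response using actual dose times are untouched. Priority: consider.

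**What to change.** - In SAP 7.7, define Ctrough by time since the last active dose: 168 h in the weekly arm and 336 h in the EOW arms. For the EOW arms this gives Days 15, 29, 43, 57, 71, 85, 113, 141 and 169.
- Report EOW samples from Days 50, 64 and 78 separately as 7-day post-dose concentrations. In the weekly arm they remain troughs.
- Reconcile footnote a, the pre-dose label on Days 50, 64 and 78, and the Day 169 nominal time in Table 5.5.3 with the EOW schedule in Section 4.5.1.

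The cost is a few lines of SAP text and a table clarification. No samples are added, and dosing and visits do not change. The calculation needs the actual dosing records and the unblinded assignment of active and placebo injections.

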5.5.4 Pharmacokinetic Sample Analyses

The serum samples will be analyzed for BMS-931699 by a validated LC-MS/MS assay. Pharmacokinetic samples collected from a subject who received placebo will not be analyzed.

In addition, serum samples will be archived for potential exposure biomarker response analysis, if the need arises and to the extent possible.

5.5.5 Immunogenicity Assessments

The immunogenic potential of the study medication will be assessed based on levels of anti-BMS-931699 antibodies. Serum samples will be obtained at visits defined in [Table 5.1-3](#). Only samples from the active treatment arms will be analyzed.

Validated sensitive, electrochemiluminescence (ECL) immunoassay method will be used to measure titers of anti- BMS-931699 antibodies in serum.

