- Interim analysis for futility and dose adaptation on BICLA response, SRI response, ACR28 and some SLE biomarkers (such as auto-antibodies, complement levels, etc.) with possible exploratory exposure response analysis, will be performed when approximately 30 subjects per arm have reached Study Day 85 (12 weeks), including subjects from Part 1 and Part 2, of treatment or have discontinued prior to reaching study Day 85. Analysis will be performed by an unblinded Sponsor team, while maintaining blind at the site and subject level. Based on the results, the dose levels and sample size may be modified.
- Ongoing assessment of safety will be performed by an independent Data Monitoring Committee (DMC) and an internal unblinded safety monitoring team. Both entities may make recommendations to the Sponsor regarding conduct of study and dose adjustment based on safety observations.

Following interim analyses and DMC reviews, dose arm(s) may be modified based on the results, as follows:

- If one or more arms are added, future randomizations will include the new arm(s).
- If one or more arms are dropped for safety reasons, randomization into that arm will be terminated and all subjects currently randomized to that or those arm(s) will be discontinued from receiving study medication.
- If one or more arms are dropped due to inadequate RO, there will be no new randomizations into that dose arm; subjects currently randomized may continue at the Investigator discretion.

The **long-term extension (LTE) period** is optional and will include eligible subjects who have completed Day 169 (week 24) of treatment and consent to participate. This period of the study will remain blinded but will no longer have a placebo arm. Eligible subjects will remain on their

originally-assigned dose arm, unless they were on the placebo arm during the short-term period. Placebo-arm subjects will be re-randomized into one of the existing active arms at Day 169 (24 weeks). Re-randomization of the placebo subjects will be done by IVRS and only the unblinded pharmacist/drug preparer will know the new randomization arm. The LTE will remain blinded to the study team and study personnel.

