1 Study procedures performed on Day 169 of the Short-Term period will be used as the starting point for LTE Day 1 procedures. They do not need to be performed twice. These are marked with an asterisk star (*).

2 Starting point for calculating the visits in LTE is the day subject performs Day 1 of the LTE.

3 Weekly SC injection required until Futility Interim Analysis. Frequency may change after the Futility Interim Analysis.

5.1.1 *Retesting During Screening*

5.1.2 *Period*

A single-retesting of laboratory parameters and/or other assessments during Screening period will be permitted (in addition to any parameters that require a confirmatory value), only if medically indicated, if there is evidence a laboratory sample was mislabeled, was inadequately processed and/or deteriorated in transit to the central laboratory.

Any new result will override the previous result (ie, the most current result prior to Randomization) and is the value by which study inclusion will be assessed, as it represents the subject's most current, clinical state. This will also apply to subjects who are being re-screened.

5.2 *Study Materials*

The site will provide all required materials for the tests performed locally (ie, relevant clinical laboratory tests). The site will have available a well-calibrated scale for recording body weight, a 12-lead ECG machine, and a calibrated sphygmomanometer and thermometer for vital signs assessments. The site will have urine collection containers, a centrifuge, a heated plaque, a monitored and alarmed refrigerator, and freezer (-20°C or below), as well as containers and dry ice for shipment and storage of blood and urine samples. The site will provide all materials required for accurate source documentation of study activities.

BMS will provide a BMS-approved protocol and any amendments or administrative letters (if required), and investigator brochure. Case report forms (electronic or hard copy) will be provided by BMS. Ten centimeter rulers will be provided by BMS for measurement of the Physician and Subject's Global Assessment of disease activity on the Case Report Form.

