8.3.2.3 Pharmacokinetic Endpoints

Ctrough: Trough level serum concentration of BMS-931699 at time points specified in Section [5.5](#).

8.3.2.5 *Immunogenicity*

Proportion of subjects with BMS-931699 induced antibody response at visit specified in [Table 5.5.3](#).

8.4 *Endpoints for Long-term Extension Period*

During the LTE period, the following endpoints will be assessed cumulatively (safety) and over time (efficacy).

8.4.1 *Safety Endpoints*

- Incidence and severity of all Adverse Events (AEs), Serious AEs, and pre-established Events of Special Interest
- Incidence and severity of clinically significant abnormalities in general laboratory tests

8.4.2 *Efficacy Endpoints*

- Proportion of subjects who achieve BICLA response (BICLA response rate)
- Proportion of subjects who meet response criteria for the SLE Responder Index (SRI) [SRI(4), SRI(5) and SRI(6)]

- CLASI score
- ACR 28 joint count of tender and swollen joints
- Overall BILAG-2004 score
- Overall SLEDAI-2K score
- Overall MDGA score
- The cumulative corticosteroid and immunosuppressant use
- Proportion of patients reaching a Major Clinical Response and Partial Clinical Response
- Fatigue, based on the FACIT
- Quality of life, based on SF-36

8.4.3 *Pharmacokinetic Endpoints*

Ctrough: Trough level serum concentration of BMS-931699 at time points specified in Section 5.5.

8.4.5 *Immunogenicity*

Proportion of subjects with BMS-931699 induced antibody response at visits defined in Table 5.1-3

8.5 *Analyses for the Short-Term Period*

8.5.1 *Demographics and Baseline Characteristics*

Frequency distributions of gender and race will be tabulated. Summary statistics for age, body weight, height, and Body Mass Index (BMI) will be tabulated.

8.5.2 *Efficacy Analyses*

Primary efficacy analysis:

The Chi-square tests will be used to compare the BICLA response rates at Day 169 between each of the active treatment arms and the placebo arm. The Chi-square p-value will be provided for each comparison between the active treatment and the placebo arm. In addition, the difference of the response rates between each active treatment and the placebo will be estimated and their corresponding 90% confidence interval will be calculated. No adjustment will be made for multiplicity.

Secondary efficacy analysis:

- Proportion of subjects who meet response criteria for the SLE Responder Index(4) [SRI(4)], SRI(5) and SRI(6) at Day 169

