### **2.3.3 *Other Unblinding Information***

For analysis of pharmacokinetic and anti-BMS-931699 samples, the Bioanalytical Sciences Group at BMS, and/or the designated vendor performing the analysis will be unblinded to the randomized treatment assignments in order to minimize unnecessary analysis of samples from control group subjects.

In collaboration with the DMC, an unblinded internal safety monitoring team, which is independent of the study team, will review the safety data throughout the study and will provide recommendations to the blinded study team. Therefore, the unblinded internal safety monitoring team can be unblinded. The unblinded internal safety monitoring team will have members from the Global Pharmacovigilance and Epidemiology group (GPV&E) within BMS.

The following BMS personnel will form the unblinded team (Independent of the blinded study team): one or more GPV&E physicians, one or more PK scientists, pharmacometrics analysts, one or more statisticians and programmers.

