## **7.9 Immunogenicity Analysis**

Serum for anti-BMS-931699 antibody titers will be drawn at Day 1, and during the ST period. Subjects who discontinue study medication will have a serum samples collected at the early termination visit and 42 days after the last dose of study medication (42 days follow up). Lack of immunogenicity is defined as the absence of a positive response.

For all summaries and listings unless specified otherwise, an anti-drug antibody (ADA) positive relative to baseline immunogenicity response is defined as:

- 1) a missing baseline immunogenicity measurement and a positive laboratory reported immunogenicity response post-baseline
- 2) a negative laboratory reported baseline immunogenicity response and a positive laboratory reported immunogenicity response post-baseline
- 3) A positive laboratory reported baseline immunogenicity response and a positive laboratory reported immunogenicity response post-baseline that has a titer value of 4 fold or greater than the baseline titer value.

All other immunogenicity measurements will be classified as negative immunogenicity response.

In addition, persistent anti-drug antibody is defined as anti-drug antibody positive occurrence relative baseline detected at 2 or more consecutive time points at least 3 months apart. Immunogenicity Frequencies

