## **8.2 Baseline Measures**

The baseline value is the last assessment taken prior to the first dose of study medication. In general, the baseline value is the assessment taken on study Day 1 before the administration of study medication unless otherwise specified.

If a measurement on Day 1 (baseline) is missing, the last assessment taken at the screening period prior to the first dose of study medication will be used.

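### Placebo subjects who cross to active drug at Day 169 have no assayed pre-drug antibody result, so the LTE endpoint cannot separate induced from pre-existing antibody in them

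*Protocol*

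**What the plan says.** **Which samples are assayed.** Protocol 5.5.5 restricts the antibody assay: "Only samples from the active treatment arms will be analyzed". SAP 2.3.3 unblinds the bioanalytical group to treatment assignment "in order to minimize unnecessary analysis of samples from control group subjects".

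**When samples are drawn.** Protocol Table 5.5.3 schedules immunogenicity samples on Days 1, 15, 29, 85 and 169, then every three months in the LTE. The Day 169 draw also serves as LTE Day 1. Footnote 1 of protocol Table 5.1-3 reads: "Study procedures performed on Day 169 of the Short-Term period will be used as the starting point for LTE Day 1 procedures".

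**Crossover.** Under protocol 3.1, placebo subjects who continue are re-randomized to an active arm at Day 169. The LTE has no placebo arm.

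**Endpoint and baseline.** The LTE immunogenicity endpoint (protocol 8.4.5) is "Proportion of subjects with BMS-931699 induced antibody response at visits defined in Table 5.1-3". Protocol 8.7.1.2 sets the LTE baseline to the original Day 1. SAP 8.2 is consistent with that: "The baseline value is the last assessment taken prior to the first dose of study medication".

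**Classification rule.** SAP 7.9 defines positivity relative to baseline in three ways. The first is "a missing baseline immunogenicity measurement and a positive laboratory reported immunogenicity response post-baseline", with no condition on titer. The second is a negative baseline followed by a positive. The third is a positive baseline followed by a positive "that has a titer value of 4 fold or greater than the baseline titer value".

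**Scope.** SAP 2.1 limits the SAP to the short-term period and sends the LTE analysis to a separate LTE SAP, which is not among the documents.

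**The concern.** Not assaying placebo samples is efficient for a subject who never receives the drug. It is less suitable once the LTE moves those subjects onto active drug, because their placebo-period samples then become their only pre-drug samples.

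An endpoint of induced response needs a comparison with the state before drug. Without an assayed pre-drug result, a positive sample after crossover may reflect a response to the drug, an antibody that was already there, or assay background. Protocol 6.7.1 has a similar dependence: it treats adverse events in subjects who develop antibodies as events of special interest, and whether an antibody developed cannot be judged without a starting value.

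If the SAP 7.9 rule is carried into the LTE, the same pre-existing antibody is also scored by two standards. An originally active subject with a positive baseline must reach a titer at least four times baseline. A former placebo subject needs only one later positive. The resulting error can only raise the count.

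**Working it through.** The documents give no figure for ADA incidence, pre-existing antibody or LTE entry, so there is no stated result to reproduce. The check is a cross-reading followed by a bound on size.

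**1. Is there an assayed pre-drug result?**
- A crossover subject's samples before active drug are Days 1, 15, 29, 85 and 169 (Table 5.5.3). All were drawn while the subject was in the placebo arm.
- LTE Day 1 is the same draw as Day 169 (Table 5.1-3, footnote 1).
- Protocol 5.5.5 excludes placebo-arm samples from assay.
- The formal baseline, original Day 1 (protocol 8.7.1.2, SAP 8.2), is therefore an unassayed sample.

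On the plain reading, no pre-drug result exists.

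**2. What would SAP 7.9 do with that?**

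| Subject with pre-existing antibody | Baseline result | Needed to be positive relative to baseline |
|---|---|---|
| Originally active | Positive | Later titer at least 4 times baseline |
| Former placebo | Missing | Any later positive |

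No placebo subject receives active drug in the short-term period, so the rule cannot mislabel a crossover subject there. Inside this SAP it reaches crossover subjects only through the LTE part of the PK sub-study (SAP 7.11.6, about 6 LTE subjects per arm), which has an immunogenicity summary.

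**3. How many subjects?**
- Placebo arm: about 70 (protocol synopsis, Number of Subjects).
- With n subjects per original arm entering the LTE and k active arms retained, the crossover share of an arm is (n/k) / (n + n/k) = 1/(k + 1).
- For n = 70 and k = 4: 70/4 = 17.5 per arm, and 17.5/87.5 = 20%.
- For k = 3 the share is 1/4 = 25%. For k = 2 it is 1/3 = 33%.
- If only 60% enter from every arm, n = 42 and there are 10.5 crossovers per arm. The share stays at 20% for k = 4.

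**4. How large is the inflation if rule 1 applies?** Let p be the prevalence of pre-existing antibody, which the documents do not give. Mislabelled subjects = 70p. Arm-level inflation with four arms = 0.20p.

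| Assumed p | Mislabelled, of 70 | Added to each arm's rate |
|---|---|---|
| 2% | 1.4 | 0.4 points |
| 5% | 3.5 | 1.0 point |
| 10% | 7 | 2.0 points |
| 20% | 14 | 4.0 points |

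Within the crossover subgroup the inflation is the full 2 to 20 points. With two arms and p = 20%, the arm-level figure is 20/3 = 6.7 points.

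These are upper bounds. They assume that all 70 enter, that every pre-existing antibody is detected after crossover, that none of these subjects has a true four-fold rise (such a subject would be correctly positive), and that crossovers are pooled with originally active subjects.

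**5. Which outputs depend on it?** In SAP 7.11.4 the concentration, efficacy and adverse event listings use laboratory-reported positivity, as does the titer listing in SAP 7.9.1. A missing baseline changes none of them. The list of neutralizing-positive subjects and the optional Ctrough plots use positivity relative to baseline, so they could be affected wherever they include crossover subjects.

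**The case against.** **The SAP rule is not an LTE rule.** SAP 2.1 confines the document to the short-term period, and protocol 8.7.1 defers LTE endpoints, analyses and treatment grouping to the LTE SAP. That plan may use another ADA rule, another baseline, or a separate placebo-to-active group. Protocol 8.7.1.5 itself plans only an incidence of positive response, with no rule relative to baseline. This stands. A reader might infer that crossover subjects will be labelled as induced under SAP 7.9 in the main LTE analysis, but the documents do not show that. The core gap does not depend on it. The assay restriction, the LTE baseline and the induced-response endpoint are all in the protocol, and no analysis rule can recover a result that was never assayed. It can only count these subjects as positive, count them as negative, set them apart or exclude them.

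**LTE Day 1 might count as an active-arm sample.** Protocol 5.5.5 points to Table 5.1-3, the LTE schedule, and the LTE has no placebo arm. SAP 2.3.3 speaks only of minimizing unnecessary analysis. The reading is possible, but no section states it, and the draw is the placebo-arm Day 169 sample. Even if assayed, it would not be the baseline under protocol 8.7.1.2 or SAP 8.2.

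**The effect is small and rests on assumptions.** This also stands. The LTE analysis is descriptive, prevalence is undocumented, and the figures above are upper bounds.

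**Listings.** A reader might infer that the error spreads to the adverse event and concentration listings for antibody-positive subjects. It does not, because those use laboratory-reported positivity.

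**Conclusion.** The point holds in a limited form. As written, the plan leaves re-randomized placebo subjects without an assayed pre-drug antibody result, and the LTE endpoint in protocol 8.4.5 cannot distinguish induced from pre-existing antibody in them. This concerns at most about 70 subjects, about 20% of each LTE arm if four arms continue with equal entry.

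The numerical inflation, at most about 0.4 to 4 percentage points per arm, is conditional on two things the documents do not settle: an assumed prevalence of 2% to 20%, and adoption of the SAP 7.9 missing-baseline rule in the LTE analysis. Short-term immunogenicity results are unaffected, because active-arm Day 1 samples are assayed.

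This is a cheap improvement that makes an existing endpoint interpretable. It does not call the trial's main conclusions into question.

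**What to change.** 1. In protocol 5.5.5, and to match in SAP 2.3.3, require assay of the last sample before first active dose for every placebo subject who enters the LTE. That is the Day 169/LTE Day 1 sample or, if it is missing, the latest earlier placebo-period sample. State that these samples are to be retained until assayed.
2. In protocol 8.7.1 and the LTE SAP, define that result as the ADA baseline for these subjects, in place of original Day 1. Make the same change in SAP 7.11.6 for the PK sub-study. The assay alone is not enough while baseline stays at Day 1.

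If the SAP 7.9 rules are used, the second and third then apply to crossover subjects, and the first is left for samples that are truly missing.

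**Cost.** At most about 70 extra assays, plus wording changes. The samples are already scheduled, so there is no new visit or draw. The documents do not say how long placebo antibody samples are kept, so availability should be confirmed for any subject who has already crossed over. SAP 2.3.3 already unblinds the laboratory, so no further unblinding is needed.
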